### Schedule of Activities Footnotes

1	Screening activities can occur up to 3 days prior to study drug administration, except for COVID-19 testing (see footnote #4), screening labs (see footnote #17) and chest x-ray or CT scan (see footnote #6). Subject eligibility should be confirmed at Day 1 prior to study drug administration.
2	For hospitalized subjects, this visit will include activities listed. For subjects discharged before Day 15, the Day 15, 22 and 29 visits may be conducted by phone and will not include any laboratory tests, vital signs, or body temperature. For subjects who remain hospitalized after Day 29, the same assessments should be completed on a weekly basis.
3	At the time of discharge, complete ONLY the Date of Discharge / UNS visit assessments on the discharge date (ie, study day assessments are not required). If a subject is discharged and the Investigator judges that it is not safe for the subject to return to the site, or the subject is not willing to return to the site, the required visits (Days 15, 22, 29, 60 and 90) that occur thereafter may be done by phone call follow-up and lab tests will not be performed.
4	Subjects must have a positive SARS-CoV-2 (2019-nCoV) test within 14 days prior to randomization. It does not have to be the first positive test but a positive test is required within 14 days prior to randomization. The test may be performed locally (at the clinical site or from another institution) or by central laboratory if local testing is not available. If SARS-CoV-2 testing is completed post-screening, please enter data into the eCRF.
5	If there is a 1-point worsening in NIAID scale in a subject, it is recommended to re-assess qSOFA (Cohort 1) or SOFA (Cohort 2) at the time of worsening or as per standard of care during hospitalization.
6	Screening x-ray or CT can be done within 7 days from randomization. If performed at additional timepoints by the Investigator/site staff as part of standard of care through Day 29, results will be collected and entered into the eCRF.
7	The discharge X-ray can be done within 72 hours of discharge.
8	Panel includes influenza – A/H3N2, A/H1N1pdm09, A/H7N9, A/H5N1, A, not typed, B, or other (specify); coronavirus – novel CoV, MERS CoV, other CoV (specify); RSV; adenovirus; bacteria; other infectious respiratory diagnosis (specify); clinical pneumonia.
9	Tuberculosis screening is mandatory for South Africa sites and is at the discretion of the Investigator elsewhere. If required, one positive (or 2 indeterminate) interferon gamma release assay test results or one positive PCR test is exclusionary.
10	The NIAID score should be recorded at the time of randomization for all eligible subjects. For subjects in Cohort 1 only, also record 1) either PaO 2 (mmHg), if available, or SpO 2 (%), and 2) FiO 2 (%) for subjects on assistive ventilation or L/min of oxygen supplementation for subjects not on assistive ventilation (e.g., simple mask/cannula). Initiation of study drug administration should occur within 24 hours of randomization.
11	If the subject remains hospitalized after Day 8 these assessments should be collected daily until the day of discharge (ie, Days 9-14, 16-21, 23-28 or after Day 29). On Day 1, assessments should be collected at the time closest to and prior to the initiation of study drug administration. Daily collection guidelines after Day 1: collect assessment in the morning at approximately the same time each day and closest to the collection of the NIAID score assessment, except for respiratory parameters (see footnote #16)
12	If available, ECHO performed from 90 days prior to randomization through Day 90 will be collected (report only).
13	If discharged, these assessments must be performed via phone call at Days 15, 22, and 29.
14	The NIAID at discharge to home should reflect status immediately post-discharge (ie, either 7 or 8).
15	Collect ventilation supportive measures (eg, pronation, nitric oxide use, tracheostomy) received by subjects on mechanical ventilation; details in the Site Manual.
16	Respiratory function parameters will be recorded daily until the date of Discharge. Daily values based on the highest daily FiO 2 , including PaO 2 , FiO 2 , SpO 2 and oxygen requirement. Other arterial blood gas parameters if available should be recorded. In addition, other supportive measures including pronation, neuromuscular blockade, tracheostomy, ECMO, vasopressor or inotropic therapy, inhaled nitric oxide or other should be recorded.

Global Version 6 (Amendment 5)

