Adverse events 	X	Continuous collection during hospitalization											X	X	X
Concomitant medications 		Continuous collection during hospitalization											X	X	X
Health care resource utilization 	X	Continuous collection during hospitalization											X	X	X
Assessment of survival 										X	X	X	X	X	X

X = required assessment for all subjects; may be collected remotely if subject has been discharged and is unable to be evaluated at the clinical site  
O = optional assessment for subjects, including those discharged from hospital and are unable to be evaluated at the clinical site, or as per standard of care  
CRP = C-reactive protein; INR = international normalized ratio; LDH = lactate dehydrogenase; SOFA/qSOFA = (quick) Sequential Organ Failure Assessment; TNF = tumor necrosis factor; WOCBP = women of childbearing potential; UNS = unscheduled visit

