In one of the first reports on the disease, Huang et al. illustrated that subjects ( $n = 41$ ) suffered from fever, cough, dyspnea, and myalgia or fatigue (Huang). Chest computerized tomography (CT) scans showed pneumonia with abnormal findings in all cases. The clinical spectrum of COVID-19 varies from asymptomatic or pauci-symptomatic forms to clinical conditions characterized by respiratory failure that necessitates mechanical ventilation and support in an intensive care unit (ICU), to multi-organ and systemic manifestations in terms of sepsis, septic shock, and multiple organ dysfunction syndromes (MODS). About a third of subjects required ICU care and 15% of cases were fatal. Similarly, in a more recent report of 201 hospitalized subjects, 41.8% developed ARDS and 52.4% of these subjects died (Wu Z, 2020).

Two recent studies provide valuable insight into the natural history of hospitalized subjects with COVID-19. The International Severe Acute Respiratory and Emerging Infection Consortium (ISARIC) COVID-19 Report is updated regularly. As of 27 April 2020, the cohort constituted 19,463 individuals with a median age of 71 years (range of 0–104 years) from centers predominantly in the United Kingdom (ISARIC, 2020). Among subjects for whom outcome data were available ( $n = 11,873$ ) there were a total of 4,278 deaths (19.5%). The mean number of days from hospital admission to outcome (death or discharge) was 8.7 days (standard deviation [SD] = 8.1 days). A total of 3,752 subjects were admitted into an ICU or high dependency unit (HDU), and of these, 989 died (26.4%). Among ICU/HDU subjects for whom outcome and treatment details were available ( $n = 1,804$ ), 54.1% received invasive mechanical ventilation (IMV). The risk of death increased with increasing age. The median length of stay was 6 days. By day 15 following admission, the proportion of subjects who died, who were in the ICU, and who were discharged leveled out, suggesting that this time point is potentially important for determining the possible therapeutic impact of a drug.

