### **Rationale for Dose and Route of Administration**

The dose rationale, and by extension the IV route of administration for COVID-19 subjects, is based on a combination of data from prior safety and efficacy evaluation of single and multiple doses in RA patients, the assessment of mavrilimumab lung distribution and pharmacodynamic effects in mice, and results from the Phase 2 portion (Cohort 1) of study KPL-301-C203.

In a Phase 1 single-ascending-dose (SAD) study, the pharmacokinetics (PK) of mavrilimumab were tested at IV doses of 0.01-10 mg/kg in subjects with mild-to-moderate RA. Mavrilimumab was well tolerated at all dose levels (Burnester GR, 2011). Pharmacokinetic and pharmacodynamic simulations from studies in subjects with RA, coupled with the PK data from

the Phase 1 study, indicate that a single dose of  $\geq 3$  mg/kg will provide EC90 (the concentration that leads to 90% maximal response) for the RA endpoint ACR50 (American College of Rheumatology 50% response criteria; data on file) for up to 22 days. Therefore, at doses  $\geq 3$  mg/kg IV, the pharmacologic profiles indicated sustained peripheral inhibition of the GM-CSF-R $\alpha$  signaling axis for at least three weeks. In the COVID-19 expanded access protocol conducted in Italy, a single-dose IV infusion of 6 mg/kg mavrilimumab was well-tolerated in 13 non-ventilated COVID-19 subjects. There did not appear to be any adverse safety signal on laboratory measures (eg, liver function tests) or AEs of special interest.

**In preclinical studies**, the potential systemic effects of mavrilimumab have been investigated in a 4-week and an 11-week repeat-dose cynomolgus monkey study. There were no effects attributable to IV administration of mavrilimumab in doses up to 100 mg/kg/week for 4 weeks in a study conducted in accordance with Good Laboratory Practice (GLP). In an 11-week exploratory (non-GLP) study there were no effects attributable to IV administration of mavrilimumab following 10 mg/kg/week, and the no observed AE level was 100 mg/kg/week. An immunocytochemistry screen to test in vitro binding of mavrilimumab to a panel of normal human tissues revealed no non-specific or unanticipated binding of the antibody. Further details on safety studies in animals and humans are provided in the Investigator's Brochure.

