## **12.2. Adverse and Serious Adverse Events**

### **12.2.1. Definition of Adverse Events**

#### **12.2.1.1. Adverse Event (AE)**

An AE is any untoward medical occurrence (eg, any unfavorable and unintended sign [including abnormal laboratory findings], symptom or disease) in a clinical investigation subject after providing written informed consent for participation in the study. Therefore, an AE may or may not be temporally or causally associated with the use of a medicinal (investigational) product.

Abnormal laboratory values or test results constitute AEs only if they fulfill at least one of the following criteria:

- they induce clinical signs or symptoms
- they are considered clinically significant
- they require therapy

Clinically significant abnormal laboratory values or test results must be identified through a review of values outside of normal ranges/clinically notable ranges, significant changes from baseline or the previous visit, or values, which are considered non-typical in subjects with the underlying disease.

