### **5.8.2. Clinical Laboratory Parameters**

The following laboratory tests are performed at the Study Site/Clinic laboratories and recorded on the eCRF:

- Screening for tuberculosis
- Pregnancy
- SARS-CoV-2 test with RT-PCR
- Hematology: complete blood count + differential
- Chemistry: electrolytes, blood urea nitrogen, glucose, and CR
- Liver profile: AST, ALT, Alb, AlkP, Tbili, Dbili
- Lipid panel: Cholesterol, total; high-density lipoprotein (HDL) cholesterol; low-density lipoprotein (LDL) cholesterol (calculation); triglycerides; very low-density lipoprotein (VLDL) cholesterol (calculation)
- Urinalysis
- [REDACTED]

The following tests are performed by the central lab:

- Respiratory Viral Panel
- Anti-mavrilimumab Antibody

- [REDACTED]

Continuous laboratory data ([REDACTED], anti-mavrilimumab antibody, hematology, coagulation, chemistry, liver profile, and lipid panel) will be examined for trends using descriptive statistics of actual values and changes from baseline over time by treatment for the safety analysis set.

Shift tables will be produced for hematology and chemistry.

All laboratory results will be presented in by-subject listings.

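### Neutropenia and drug-induced liver injury are counted over all dosed subjects, although required blood sampling depends on when a subject leaves hospital; the size and direction of any bias are unknown

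*Combined protocol and SAP*

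**What the plan says.** **Sampling.** Protocol Tables 2 and 4 schedule hematology and liver profile at Days 3, 15 and 29 and at the Discharge/UNS visit, with Days 60 and 90 optional. The Table 2 legend reads: "X = required assessment for all subjects; may be collected remotely if subject has been discharged". Footnote 2 says of subjects discharged before Day 15 that "the Day 15, 22 and 29 visits may be conducted by phone and will not include any laboratory tests, vital signs, or body temperature". It also asks for weekly assessments in subjects still in hospital after Day 29. Footnote 3 is conditional: if return is judged unsafe or the subject declines, later visits "may be done by phone call follow-up and lab tests will not be performed". Section 12.1.5 repeats that condition. It also lets the investigator order further laboratory tests up to Day 29, which must be recorded. Footnote 13 has adverse events collected by phone at Days 15, 22 and 29 after discharge.

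**Definitions.** Section 12.2.1.3 makes two laboratory-based conditions adverse events of special interest (AESIs). Neutropenia is ANC below 1.0 × 10^9/L. DILI is ALT or AST above 3 × ULN with bilirubin above 2 × ULN if liver function was normal at baseline, or a doubling if it was abnormal. The findings must fall within 8 days of each other and have no other explanation.

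**Analysis.** In the Phase 3 SAP, Section 5.8.1 tabulates treatment-emergent AESIs by SOC and PT, with onset up to 90 days after dosing. Section 3.2 puts every dosed subject in the denominator. Section 4 restricts by-visit tables to scheduled visits. On laboratory data, Section 5.8.2 says: "Shift tables will be produced for hematology and chemistry". The liver profile is a separate item in that section and is not named there. Sections 4.6 and 6 limit laboratory summaries at the first database lock to baseline values, while adverse events are tabulated through Day 29.

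**The concern.** A phone call cannot find a low neutrophil count or a rise in transaminases and bilirubin unless someone has drawn blood. Whether blood is drawn after the first days depends on discharge, which happens after randomization and which treatment may change. Phase 3 SAP Section 5.7.2 itself treats discharged subjects as responders when no NIAID score is available in the window. Death also ends sampling.

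Two arms with the same true risk could therefore show different AESI counts because one was tested more often. The planned table gives no number tested, number of draws or time under laboratory observation, so a reader could not separate a difference in risk from a difference in testing. Neutropenia is a named potential risk in Section 4 of the protocol, which already draws reassurance from between-arm safety counts in Phase 2.

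**Working it through.** The documents give no figure for discharge by arm, AESI rate or sampling intensity, so there is nothing of the plan's own to reproduce. The check counts scheduled draws and then asks what unequal discharge could do.

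**1. Required post-dose hematology/liver draws to Day 29** (Tables 2 and 4, footnotes 2 and 3)

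| Course | Draws | Number |
|---|---|---|
| Discharged Days 4–14 | Day 3, discharge | 2 |
| Discharged Days 16–28 | Days 3 and 15, discharge | 3 |
| In hospital to Day 29 | Days 3, 15, 29, then weekly | 3 or more |
| Death between Day 4 and Day 14 | Day 3 | 1 |

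**2. Exposure.** Section 12.5.1 gives a half-life of about 15 days. With simple exponential decline, 0.5^(8/15) = 69% remains 8 days after dosing and 0.5^(29/15) = 26% after 29 days. Drug is still present after an early-discharged subject's last required draw.

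**3. Detection model (all inputs assumed).** The true risk is equal in both arms. Onset is uniform over the 28 days from Day 1 to Day 29, the abnormality lasts L days (3 to 10), and it is found only at a scheduled draw. Detection probability = (days of onset that a draw would catch) / 28.

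- Discharged on Day 8, e: L = 3 gives (2 + 3)/28 = 0.18; L = 10 gives 7/28 = 0.25.
- In hospital to Day 29, h: L = 3 gives (2 + 3 + 3)/28 = 0.29; L = 10 gives (2 + 10 + 10)/28 = 0.79.
- Death on Day 12, d: 2/28 = 0.07.

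With a fraction f discharged early and a fraction m dying early, the detected share of true events is f·e + m·d + (1 − f − m)·h. The apparent risk ratio is this quantity for active divided by that for placebo.

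Worked case, L = 10, 70% v 60% discharged early, no early deaths: active 0.70 × 0.25 + 0.30 × 0.787 = 0.411; placebo 0.60 × 0.25 + 0.40 × 0.787 = 0.465; ratio 0.885.

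| Early discharge, active v placebo | Early deaths, active v placebo | Apparent ratio, L = 3 to 10 |
|---|---|---|
| 65% v 60% | none | 0.94–0.98 |
| 70% v 60% | none | 0.89–0.95 |
| 75% v 60% | none | 0.83–0.93 |
| 70% v 60% | 5% v 10% | 0.96–1.00 |
| 70% v 60% | 5% v 15% | 1.05–1.07 |

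The rows with deaths overstate the offset, because they count onsets after death as missed events. They do show that the direction is not fixed.

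**4. A more extreme illustration.** Assume 4% true neutropenia in Days 15–29 in both arms, no detection after discharge, and 80% v 65% discharged before Day 15. Detected rates are 4% × 0.20 = 0.8% and 4% × 0.35 = 1.4%, a ratio of 0.57. With 75% v 70% the ratio is 1.0%/1.2% = 0.83; with equal discharge it is 1. With 581/3 = 193.7 subjects per arm (Phase 3 SAP Section 1.4), 0.8% v 1.4% is about 1.5 v 2.7 subjects.

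**5. The sampling rule.** Footnote 2 excludes labs at Days 15–29 for everyone discharged before Day 15. Footnote 3 and Section 12.1.5 exclude them only if the subject does not return. The legend calls the same cells required for all. Sites could apply different rules.

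**The case against.** **Sampling does not stop outright.** This stands. Footnote 2 says phone visits may be used, footnote 3 is conditional, discretionary labs to Day 29 must be recorded, and Day 60 and 90 draws are optional. What ends is required sampling. Footnote 17, attached to the hematology and liver row, is not in the text available here and could qualify this.

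**A reader might infer that the arm discharged sooner will look safer.** The documents do not support that. Every rate above is assumed, and early deaths can cancel or reverse the effect. The 0.57 ratio covers Day 15–29 onsets only and leaves out what the Day 3 and discharge draws would find, so it should not be read as an estimate.

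**A reader might infer that an asymptomatic low ANC need not be reported,** since Section 12.2.1.1 says "Abnormal laboratory values or test results constitute AEs only if they fulfill at least one of the following criteria". The specific rules largely answer this: Section 12.2.1.3 makes ANC below the threshold an AESI reportable within 24 hours, and the SAE exceptions text in Section 12.5 says severe neutropenia is to be reported as an SAE.

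**DILI is not purely numeric.** Correct. It requires the absence of another explanation, and eligibility admits AST and ALT up to 10 × ULN. A flat 3 ×/2 × ULN flag would count subjects already above those limits at entry and could miss doublings.

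**Some context is borrowed.** The Section 4 statement "The median length of stay was 6 days" describes an external hospital cohort, and the pharmacology behind "signaling axis for at least three weeks" comes from rheumatoid arthritis. Neither shows when these events would occur in this trial.

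**Safeguards exist.** Safety analysis is descriptive, laboratory summaries show non-missing n, and all results are listed by subject. These help at the second lock. They do not put the number tested beside the AESI counts, and no post-baseline laboratory summary is planned at the first lock.

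**Conclusion.** The concern holds as one of unequal ascertainment. Required sampling for two laboratory-dependent AESIs depends on discharge and survival, and the planned crude incidence over all dosed subjects does not show this. If discharge or death timing differs by arm, the comparison is confounded by testing. If it does not, there is no distortion from this source.

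Size and direction cannot be determined from the documents. Under the assumptions above, the apparent ratio with no true difference is 0.83 to 0.98 without early deaths; with early deaths added to the 70% v 60% case it lies between 0.96 and 1.07. Event counts may also be very small. Efficacy analyses are not affected. This is a cheap improvement to safety reporting, and nothing here shows that the trial's safety conclusions favor the drug.

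**What to change.** **1. Phase 3 SAP Sections 5.8.1 and 5.8.2.** Keep the treatment-emergent AESI table over all dosed subjects. Add a supplementary table from all recorded post-baseline results, scheduled and unscheduled, giving per arm:

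- the number with any ANC below 1.0 × 10^9/L;
- the number meeting the laboratory part of the protocol's DILI definition (3 ×/2 × ULN if normal at baseline, doubling if abnormal, within the 8-day window), labelled as laboratory criteria and not as adjudicated DILI;
- the number sampled and the number of draws in each window, with results among those sampled, and separately for the common early window at Day 3.

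Add the liver profile to the shift tables.

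*Cost:* a few programmed tables from data already collected. Denominators of sampled subjects are themselves selected, so they supplement the main table and do not replace it. Post-baseline labs are not cleaned until the second lock, so the table would come then or need earlier cleaning.

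**2. Protocol.** Footnotes 2 and 3, Section 12.1.5 and the Table 2 legend must be reconciled on whether laboratory tests apply to discharged subjects who can return. Which rule is right is for the sponsor to decide.

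*Cost:* a wording change.

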### 3. LIST OF ABBREVIATIONS AND DEFINITIONS OF TERMS

The following abbreviations and specialist terms are used in this study protocol.

**Table 3: Abbreviations and Specialist Terms**

Abbreviation or Specialist Term	Explanation
2019-nCoV	2019 novel coronavirus
AE	Adverse event
AESI	Adverse event of special interest
ALT	Alanine aminotransferase
ARDS	Acute respiratory distress syndrome
AST	Aspartate aminotransferase
BAL / BALF	Bronchoalveolar lavage / bronchoalveolar lavage fluid
CFR	Code of Federal Regulations
CMH	Cochran-Mantel-Haenszel
COVID-19	Corona Virus Disease 2019
CRF	Case report form
CRO	Contract research organization
CRP	C-reactive protein
CRS	Cytokine release syndrome
CT	Computerized tomography
DILI	Drug-induced liver injury
DMC	Data Monitoring Committee
ECG	Electrocardiogram
ECMO	Extracorporeal membrane oxygenation
eCRF	Electronic case report form
FiO 2	Fraction of inspired oxygen
GM-CSF	Granulocyte-macrophage colony-stimulating factor
ICH	International Council on Harmonisation
ICU	Intensive care unit
IEC	Independent Ethics Committee
IFN-γ	Interferon-gamma
IgG	Immunoglobulin G
IL	Interleukin
IMV	Invasive mechanical ventilation
IND	Investigational New Drug Application

Abbreviation or Specialist Term	Explanation
IRB	Institutional Review Board
ISARIC	International Severe Acute Respiratory and Emerging Infection Consortium
ITT	Intent-to-treat
IUD	Intrauterine device
IUS	Intrauterine hormone-releasing system
IV	Intravenous
IWRS	Interactive web-based response system
LDH	Lactate dehydrogenase
MERS	Middle East respiratory syndrome
mITT	Modified intent-to-treat
MMF	Mycophenolate mofetil
MODS	Multiple organ dysfunction syndromes
NIAID	National Institute of Allergy and Infectious Diseases
NIV	Non-invasive ventilation
PaO 2	Partial pressure of oxygen
PCR	Polymerase chain reaction
PK	Pharmacokinetics
RA	Rheumatoid arthritis
RO	Receptor occupancy
SAD	Single-ascending-dose
SAE	Serious adverse event
SAP	Statistical analysis plan
SARS-CoV-2	Severe acute respiratory syndrome coronavirus 2
SD	Standard deviation
SOFA / qSOFA	Sequential Organ Failure Assessment / quick SOFA
SpO 2	Oxygen saturation
SUSAR	Suspected unexpected serious adverse reaction
TB	Tuberculosis
TNF	Tumor necrosis factor
ULN	Upper limit of normal
UNS	Unscheduled site visit
US	United States

